1 PROTOCOL SUMMARY

1.1 SYNOPSIS

Title:	Comparative Effectiveness of Two Letters to Encourage Judicious Prescribing of Opioids: A County-wide Project in Los Angeles
Grant Number:	P30AG024968
Study Description:	In collaboration with the Los Angeles County Medical Examiner's Office and the State of California's controlled Substance Utilization Review and Evaluation System (CURES), the investigators propose to review opioid poisonings over 12 months and send letters to prescribers in California when at least one of the provider's prescription(s) was filled by a patient who died of an opioid poisoning in Los Angeles County. The letters will be non-judgmental and factual, explaining that a patient of the provider who was being treated with prescription narcotics died of an opioid poisoning. The letters will also encourage judicious prescribing including use of the CURES system before prescribing. The investigators will evaluate physician prescribing practices over 24 months (12 months pre- and 12 months post-letter) using data from the CURES database. The hypothesis is that letters will make the risk of opioids more cognitively available and that physicians will respond by prescribing opioids more carefully, resulting in fewer deaths due to misuse and more frequent use of the CURES system.
Objectives*:	
1) To conduct a randomized trial comparing two versions of a letter sent to prescribers in Los Angeles County notifying them that one of their prescriptions was filled by a patient who died of an opioid poisoning, and2) Evaluate the effects of the randomized trial and identify factors that predict intervention effectiveness.
Endpoints*:	
1) Average change over time in Milligram Morphine Equivalents (MME) dispensed2) Average change over time in Benzodiazepine Equivalents (BE) dispensed
Study Population:	Los Angeles County prescribers
Phase* or Stage:	IV
Description of Sites/Facilities Enrolling Participants:	Los Angeles County Medical Examiner's Office

Description of Study	We will conduct a randomized trial to test the two versions of a letter signed by the Chief Medical Examiner-Coroner and County Health Officer of Los Angeles County to notify prescribers of the death in their practice. Each letter version includes the decedent's name, date of birth and date of death, and outlines the annual number and types of prescription drug deaths seen by the medical examiner, discusses the value of and way to access the State's prescription drug monitoring program and includes five CDC guideline-recommended safe prescribing strategies: 1) Avoid co-prescribing of opioids with benzodiazepines, 2) prescribe minimal dose necessary for acute pain, 3) consider slow tapers with pauses to below 50 MME per day, 4) avoid prescriptions lasting greater than 3-months for pain, and 5) prescribe naloxone in conjunction with opioids for patients taking > 50 MME per day. Each letter also states that CURES review is required by law as of October 2, 2018.
Intervention/Experimental Manipulation:	
Study Duration*:	24 months
Participant Duration:	24 months

1.2 SCHEMA

1.3 SCHEDULE OF ACTIVITIES

Assessment	Enrollment	Randomization	Baseline	Intervention Period	Observation Period	Follow-up Period
	January 2019 to July 2020	Monthly: 12 months prior April 2019 to to decedent July 2020 date of death (DOD)		1-6 months after DOD	2-13 months after Letter is sent	> 13 months after letter is sent
Data attainment on demographics	X	X	X			
Inclusion/Exclusion Criteria	X					
Data attainment on controlled substances			X	X	X	
Data analysis						X

2 INTRODUCTION

2.1 STUDY RATIONALE

One promising strategy for changing physician behavior is through use of “nudges”. The term “nudge” identifies a set of social and cognitive devices that persuade decisions in subtle ways while preserving choice. When prescribing narcotics, physicians may not have recent experiences that come to mind as to why these drugs are dangerous, making risks seem remote. They may also not consult data on a patient’s other narcotic prescriptions in their State’s pharmaceutical drug monitoring program. One useful nudge capitalizes on a finding called “Availability”. Availability is the notion that people rely upon knowledge that is salient, recent and readily available to them to evaluate risks and make decisions. If a physician issued a prescription for a narcotic that resulted in a recent opioid poisoning, providing that physician with this feedback may make the physician more likely to consult a pharmaceutical drug monitoring program database and also prescribe more judiciously.

We published a randomized trial in the journal *Science* demonstrating that carefully crafted letters, supportive in tone and designed to increase the availability of patient harms, are effective in reducing opioid prescribing among high risk prescribers (i.e., those with a death in their practice).⁹ Milligram morphine equivalents in prescriptions filled daily by patients of letter recipients compared to controls decreased by 9.7% (95% confidence interval: 6.2 to 13.2%; $p < 0.001$) over a 3-month period following intervention (Figure 2). We also observed both fewer high dose prescriptions and new patients started on opioids among letter recipients. Learning of a patient's fatal overdose may instill safe opioid prescribing habits in physicians.

Figure 2. Adjusted milligram morphine equivalent prescriptions

Parameter	Randomization group	
	Letter	Control
Prescribers followed	388	438
Preintervention	72.5 (71.3 to 73.7)	71.6 (70.3 to 72.8)
Postintervention	65.7 (63.8 to 67.5)	71.7 (70.0 to 73.5)
Increment (pre- to post-)	-6.8 (-9.9 to -3.8)	0.1 (-2.8 to 3.2)
Difference in increment	-6.9 (-13.1 to -1.0)	
P value	0.001	

2.2 BACKGROUND

Much of the increase in opioid prescribing rates from 1999 until the past decade has been driven by an increase in the use of prescription opioids to treat non-cancer pain (*Guy et al. 2017; Boudreau et al. 2009*). Although opioids carry significant risks of overdose and addiction, they are no more effective for treating chronic non-cancerous pain over a one year period than non-opioid alternatives (*Krebs et al. 2018*). The greater availability of prescription opioids has been accompanied by an alarming rise in the negative consequences related to opioid use. In 2017, there were 17,029 prescription opioid overdose deaths in the US (*Scholl 2019*). The costs of prescription opioid adverse outcomes are staggering. Aggregate costs for prescription opioid harms are estimated at over \$78.5 billion (in 2013 USD) and 25% of the aggregate economic burden is publicly funded (i.e., Medicaid, Medicare, and veterans' programs) (*Florence et al. 2016*).

In 2016, the Centers for Disease Control and Prevention (CDC) issued the "CDC Guideline for Prescribing Opioids for Chronic Pain" which encourages the use of alternatives to opioids and other practices that minimize harm to patients (*Dowell et al. 2016*). Despite the introduction of this guideline, primary care clinicians, who prescribe 45% of all opioid prescriptions in the US, report challenges in following these recommendations (*Kroenke et al. 2019*). The dynamics of opioid use make following guidelines difficult. Since opioid analgesia from a given dose declines with chronic use due to opioid tolerance, doses increase and the chance of harm grows. Over time, the primary benefit of opioids for many patients becomes the avoidance of withdrawal. As patients become dependent on opioids, they may misconstrue the treatment of interdose withdrawal hyperalgesia as ongoing effectiveness and they may become reluctant to stop

opioids (*Juurlink 2017*). More cautious opioid prescribing (including fewer new starts, avoidance of high doses, and slow, collaborative tapers for those already on high dose long-term therapy) can improve the balance of benefits and harms for patients with chronic pain. To embrace more cautious prescribing, a clinician may need to be informed that opioid risks are present and relevant to his/her own patients.

2.3 RISK/BENEFIT ASSESSMENT

2.3.1 KNOWN POTENTIAL RISKS

There is a small risk that people who are not connected with this study will learn a participant's identity or their personal information. Physicians may also experience some discomfort in learning that a patient that they prescribed to has died.

2.3.2 KNOWN POTENTIAL BENEFITS

Clinicians may benefit if the quality of care they provide their patients is improved by the intervention. They also may learn more about guidelines for appropriate prescribing.

2.3.3 ASSESSMENT OF POTENTIAL RISKS AND BENEFITS

In sum, the risks of this study are small relative to the potential benefits in increased adoption of evidence-based practices, and improved patient outcomes through improved pain management and reduction in opioid use. Unfortunately, most people who develop opioid use disorder, use illicit opiates or synthetic opioids or who die of an opioid poisoning are introduced to these drugs medically. We hope that these pilot studies will have a number of benefits that will address the unmet needs of this important group of individuals. We anticipate that health care systems, government agencies and other policy makers will benefit from implementation of the interventions we develop. Even if the intervention(s) are not found to be beneficial, then the knowledge gained will hopefully lead to new insights that will result in successful redesign for future studies. Most importantly, we anticipate the approaches we are studying will lead to fewer opioid harms, fewer persons suffering from opioid use disorder and poisoning death and fewer tragedies for families of persons who find themselves misusing opioid medications.

3 OBJECTIVES AND ENDPOINTS

OBJECTIVES	ENDPOINTS
Primary	
Evaluate the effects of the randomized trial and identify factors that predict intervention effectiveness.	Average change over time in Milligram Morphine Equivalents (MME) dispensed Average change over time in Benzodiazepine Equivalents (BE) dispensed

4 STUDY DESIGN

4.1 OVERALL DESIGN

This is a decedent-cluster randomized field experiment; clusters of prescribers within each decedent will be randomly allocated to one of two letters interventions. This design avoids treatment contamination—clinicians prescribing to the same patient will be able to share information about the intervention without diluting its effect. If two or more decedents have the same prescriber, that prescriber will be assigned to one and only one of those decedent clusters by random draw. Two factors will serve as random strata: 1) whether the decedent received a prescription from a clinician with a single or multiple deaths, and 2) whether opioids only, opioids in combination with benzodiazepines, or benzodiazepines only were the cause of death. The first strata are designed to form equivalent groups on prescriber risk posture. The second strata equate preference for type of scheduled drug prescribed in practice. Strata will be crossed to form $2 \times 3 = 6$ randomization groups.

4.2 SCIENTIFIC RATIONALE FOR STUDY DESIGN

Given the recent results collected in San Diego County that were reported by our group in *Science*,⁹ on August 14th, 2018 the Los Angeles County Board of Supervisors voted to explore the feasibility of sending letters to prescribers whose patients suffered a fatal overdose to encourage judicious prescribing. [name] participated in these discussions and helped formulate along with the County Health Officer [name], MPH and the County Medical Examiner-Coroner, [name], two versions of the letter (described below). A report was submitted to the County in September on feasibility and a “make it so” Board motion on October 2, 2018 approved sending of the letters.

4.3 JUSTIFICATION FOR INTERVENTION

In 2016, the Centers for Disease Control and Prevention (CDC) issued the “CDC Guideline for Prescribing Opioids for Chronic Pain” which encourages the use of alternatives to opioids and other practices that minimize harm to patients (*Dowell et al 2016*). Despite the introduction of this guideline, primary care clinicians, who prescribe 45% of all opioid prescriptions in the US, report practical challenges in implementing these recommendations (*Kroenke et al 2019*). The dynamics of opioid use make following guidelines difficult. Since opioid analgesia from a given dose declines with chronic use due to opioid tolerance, doses increase and the chance of harm grows. Over time, the primary benefit of opioids for many patients becomes the avoidance of withdrawal. As patients become dependent on opioids, they may misconstrue the treatment of withdrawal hyperalgesia as ongoing effectiveness, and they may become reluctant to stop opioids (*Juurlink, 2017*). More cautious opioid prescribing (including fewer new starts, avoidance of high doses, and slow, collaborative tapers for those already on high dose long-term therapy) can improve the balance of benefits and harms for patients with chronic pain. To embrace more cautious prescribing, a clinician may need to be informed that opioid risks are present and relevant to his/her own patients.

Notifying physicians via a letter of the death of their patient has been shown to significantly reduce opioid prescribing (Doctor et al. 2018). Two versions of a letter will be signed by the Chief Medical Examiner-Coroner and County Health Officer of Los Angeles County to notify prescribers of the death in their practice. Each letter version includes the decedent's name, date of birth and date of death, and outlines the annual number and types of prescription drug deaths seen by the medical examiner, discusses the value of and way to access the State's prescription drug monitoring program and includes five CDC guideline-recommended safe prescribing strategies: 1) Avoid co-prescribing of opioids with benzodiazepines, 2) prescribe minimal dose necessary for acute pain, 3) consider slow tapers with pauses to below 50 MME per day, 4) avoid prescriptions lasting greater than 3-months for pain, and 5) prescribe naloxone in conjunction with opioids for patients taking > 50 MME per day. Each letter also states that CURES review is required by law as of October 2, 2018.

Version B of the letter includes additional text involving an "if/when/then statement" along with an injunction to providers to share safety information with patients so that they identify as a "safe prescriber." The text reads as follows: *When your next patient presents with pain, keep the above 5 recommendations close at hand to assist with their safe care. Also, be comfortable voicing your concern about prescribing safety with them so that they are also aware of the dangers scheduled drugs may carry.* "If/when/then" is a form of "pre-suasion" that provides simple rules that tie goals to specific actions and has been used successfully to encourage behavior in many areas including medication adherence and drug abuse rehabilitation.²¹ Letters will be signed and posted in the U.S. mail.

4.4 END-OF-STUDY DEFINITION

A participant is considered to have completed the study if he or she has completed the baseline assessment, received a letter, and been observed for >13 months following letter receipt.

The end of the study is defined as completion of the >13-month data observation period following receipt of letter shown in the Schedule of Activities (SoA), **Section 1.3**.

5 STUDY POPULATION

We will intervene on all clinicians and allied health professionals with prescribing privileges and at least one prescription drug death over the course of a year as part of a public health program to encourage safe prescribing in Los Angeles County. Informed consent of patients and clinicians is waived under HHS regulations at 45 CFR 46.116(c), as the study was evaluating a County public service safe prescribing program. As part of the County safe prescribing program, prescribers will be identified in the Controlled Substance Utilization Review and Evaluation System (CURES) system. All California pharmacies and clinics that dispense controlled substances must submit reports to CURES on a weekly basis. In consultation with the program manager of CURES, a letter notifying CURES administrators that prescriptions from these clinicians would be evaluated prospectively after the safe prescribing letters have been sent will be submitted to the CURES system.

5.1 INCLUSION CRITERIA

The inclusion criteria for clinicians are as follows: a) must be located in Los Angeles County, b) have scheduled drug prescribing privileges and, c) have prescribed a schedule II, III, or IV drug to a person in the 12 months prior to their opioid-related death.

5.2 EXCLUSION CRITERIA

Clinicians not meeting the inclusion criteria above will be excluded from the study.

5.3 LIFESTYLE CONSIDERATIONS

Not applicable

5.4 SCREEN FAILURES

Not applicable

5.5 STRATEGIES FOR RECRUITMENT AND RETENTION

We will intervene on all clinicians and allied health professionals with prescribing privileges and at least one prescription drug death over the course of a year as part of a public health program to encourage safe prescribing in Los Angeles County. Informed consent of patients and clinicians is waived under HHS regulations at 45 CFR 46.116(c), as the study is evaluating a County public service safe prescribing program. We will utilize data from the County Medical Examiner's Office to identify opioid-related deaths and the state's prescription drug monitoring program (CURES) to identify prescribers to those decedents.

6 STUDY INTERVENTION(S) OR EXPERIMENTAL MANIPULATION(S)

6.1 STUDY INTERVENTION(S) OR EXPERIMENTAL MANIPULATION(S) ADMINISTRATION

6.1.1 STUDY INTERVENTION OR EXPERIMENTAL MANIPULATION DESCRIPTION

Two versions of a letter will be signed by the Chief Medical Examiner-Coroner and County Health Officer of Los Angeles County to notify prescribers of the death in their practice. Each letter version includes the decedent's name, date of birth and date of death, and outlines the annual number and types of prescription drug deaths seen by the medical examiner, discusses the value of and way to access the State's prescription drug monitoring program and includes five CDC guideline-recommended safe prescribing strategies: 1) Avoid co-prescribing of opioids with benzodiazepines, 2) prescribe minimal dose necessary for acute pain, 3) consider slow tapers with pauses to below 50 MME per day, 4) avoid prescriptions lasting greater than 3-months for pain, and 5) prescribe naloxone in conjunction with opioids for patients taking > 50 MME per day. Each letter also states that CURES review is required by law as of October 2, 2018.

Version B of the letter includes additional text involving an “if/when/then statement” along with an injunction to providers to share safety information with patients so that they identify as a “safe prescriber.” The text reads as follows: *When your next patient presents with pain, keep the above 5 recommendations close at hand to assist with their safe care. Also, be comfortable voicing your concern about prescribing safety with them so that they are also aware of the dangers scheduled drugs may carry.* “If/when/then” is a form of “pre-suasion” that provides simple rules that tie goals to specific actions and has been used successfully to encourage behavior in many areas including medication adherence and drug abuse rehabilitation. Letters will be signed and posted in the U.S. mail.

6.1.2 ADMINISTRATION AND/OR DOSING

Not applicable

6.2 FIDELITY

No text is to be entered in this section; rather it should be included under the relevant subheadings below. This section refers to efforts made to confirm that the intervention is appropriately conducted by the interventionist(s). It is distinct from the content of Section 6.4, Study Intervention Adherence, which is intended to capture a study participant’s adherence to an intervention.

6.2.1 INTERVENTIONIST TRAINING AND TRACKING

It is the primary role of the data analysts ([name] and [name]) to: 1) determine the appropriate number of eligible providers to reach sufficient statistical power, 2) record provider information in a secure, password protected database located at LA County Medical Examiner-Coroner’s office and, 3) track enrolled providers in regards to their intervention status and progress.

6.3 MEASURES TO MINIMIZE BIAS: RANDOMIZATION AND BLINDING

For randomization, two decedent lists will be generated from the crossed strata levels. Using random.org’s sequence generator, two true random integer sequences derived from atmospheric noise will determine decedent order in each list. For each ordered list, prescribers to decedents in the first half will receive Letter A, the second half of the list will receive Letter B.

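### Section 4.1 promises six randomisation groups but section 6.3 allocates from two half-split lists, and equation [1] carries no strata; the sections should be made to agree

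*Combined protocol and SAP*

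**What the plan says.** Section 4.1 states that "Two factors will serve as random strata". The first is whether the decedent had a prescriber with one death or with several. The second is whether "opioids only, opioids in combination with benzodiazepines, or benzodiazepines only were the cause of death". The two are crossed to give 2 × 3 = 6 groups. The section also gives the purpose: the first factor is to make the groups alike on risk posture, and of the other it says "The second strata equate preference for type of scheduled drug prescribed in practice".

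Section 6.3 describes the mechanics. It says that "two decedent lists will be generated from the crossed strata levels", that two random sequences order them, and that "prescribers to decedents in the first half will receive Letter A, the second half of the list will receive Letter B".

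On which deaths can enter, section 5 speaks of prescribers with "at least one prescription drug death over the course of a year". The inclusion criterion in 5.1 requires a controlled-drug prescription "to a person in the 12 months prior to their opioid-related death", and 5.5 uses medical examiner data "to identify opioid-related deaths".

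Equation [1] in section 9.4.1 contains time, letter, their interaction and a random intercept for prescriber within decedent. Section 9.4.2 is empty, and no analysis section mentions the strata.

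**The concern.** Section 4.1 claims a design property, balance over six crossed cells, that the procedure in 6.3 cannot guarantee as worded. Two analysts could follow 6.3 and build different lists: one per level of the single/multiple-deaths factor, some other pairing of cells, or two lists within every cell.

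Section 6.3 also has no rule for a list of odd length. It does not say whether lists are built once or in batches; the schedule in 1.3, whose table is broken in the text available, appears to say monthly.

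At stake are the comparability that 4.1 advertises, the reproducibility of the allocation, and the match between how letters are assigned and how the data are analysed.

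**Working it through.** **Count of cells and lists.** 2 levels × 3 levels = 6, which reproduces the figure in 4.1. Section 6.3 supplies 2 lists and 2 sequences. If benzodiazepines-only deaths cannot enter, as 5.1 and 5.5 suggest, 2 × 2 = 4 cells remain, still not 2. A half-split list forces balance only on the list as a whole. Two lists can therefore balance one two-level grouping, but neither six cells, nor four, nor a three-level factor.

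**Size of the chance imbalance.** Inputs:
- Decedents: 192 expected per arm (9.2), so 2 × 192 = 384.
- Assumption: neither list uses cause of death.
- Assumption: one cause-of-death level holds L = 20, 40, 80 or 120 decedents. The documents give no sizes.

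The number of that level on Letter A is hypergeometric: 192 drawn from 384, of which L are of interest. Its variance is (L/4) × (384 − L)/383. For L = 40 this is 10 × 344/383 = 8.98, so the SD is 3.00.

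| L | SD of Letter A count | P(more than 2 from L/2) | Symmetric range with at least 95% coverage |
|---|---|---|---|
| 20 | 2.18 | 0.250 | 6:14 to 14:6 (96%) |
| 40 | 3.00 | 0.404 | 14:26 to 26:14 (97%) |
| 80 | 3.98 | 0.530 | 32:48 to 48:32 (97%) |
| 120 | 4.55 | 0.582 | 51:69 to 69:51 (96%) |

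Simulating two separate half-split lists gives the same probabilities to within 0.002, whether the lists hold 192 + 192 or 288 + 96 decedents. The result does not depend on how the two lists divide the sample.

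A second setting looks at a single crossed cell inside a list of 192. A cell of 64 has a 95% range of 26 to 38 on Letter A and differs by at most 1 between letters with probability 0.12. For a cell of 19 the range is 5 to 14 (probability 0.37).

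**One list per crossed stratum.** A single half-split list per cell holds each cell to a difference of 1 by construction. With batches, this needs a rule for the odd decedent. I simulated 16 monthly batches of 24 (384/16) with assumed cell shares of 40, 25, 5, 15, 10 and 5%:
- Odd decedent alternating between letters within each stratum, first letter at random: largest difference 1 per cell, 2 per cause-of-death level and 6 over the whole trial.
- Odd decedent always to Letter B: six lists drift by about 46 decedents in total and two lists by about 16. This is close to 6 × 16 × ½ = 48 and 2 × 16 × ½ = 16, since a list is odd about half the time.

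**Extra model terms.** Six cells need 5 stratum + 5 stratum-by-time = 10 terms. Four cells need 3 + 3 = 6.

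**The case against.** *Section 6.3 does refer to the crossed strata.* Its wording is ambiguous, and the schema in 1.2 could not be read, so six lists may have been intended or used. This stands: the documents do not show that the actual allocation was unstratified. But if two is a slip for six, 6.3 is misstated; if it means one list per single/multiple-deaths level, cause of death is dropped contrary to 4.1. Either way the text needs correcting.

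*The harm is modest.* This also stands. The lists are randomly ordered, so no bias follows. The primary contrast is a difference in differences, which already removes baseline level differences; only imbalance in a factor that predicts change over time matters. The level sizes are assumed, and the threshold of 2 is a choice.

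*More lists bring their own problems.* Without an odd-length rule, six lists drift further than two. With alternation, a list of one decedent has a predictable letter. Both are fair points, and the fix has to deal with them.

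*A stronger reading on the analysis.* A reader might infer that, with stratified lists, equation [1] without strata must be conservative, and that adding strata would raise power by a predictable amount. That holds for a test on decedent-level mean change, where strata contribute to the error term. Equation [1] has a random intercept only, so the standard error of its interaction comes mainly from observation-level residual variation. In a linear, uncensored simulation of such a model under six half-split lists (384 decedents, 5 prescribers each, 12 or 180 observations per period), the size of the 5% test was 4.5% to 5.7% when decedents did not otherwise differ in change, with no trend as the strata explained more. When they did differ, it rose above nominal. The documents therefore support no claim of conservatism and no specific power gain.

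**Conclusion.** The mismatch is real: six groups in 4.1, two lists in 6.3, no text connecting them, and no strata in equation [1]. As written, balance on cause of death is left to chance if the lists do not use it. A level of 40 among 384 decedents would then split more than 2 from even about 40% of the time, and would usually lie between 14:26 and 26:14. These figures rest on the 384 decedents expected in 9.2 and on assumed level sizes.

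The consequence is chance imbalance and possibly lost precision. A reader might go further and infer a biased comparison, or that the stratification was certainly not carried out. The documents support neither. It should be corrected, but it does not threaten the validity of the randomisation.

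**What to change.** - **Sections 4.1, 5, 5.1 and 5.5:** state whether benzodiazepines-only deaths are eligible, and hence whether six or four cells can occur.
- **Section 6.3:** randomise from one list per crossed stratum that can occur. Keep the half-split, or use permuted blocks within strata.
- **Section 6.3, batches:** say whether lists are built once or monthly. Close each batch before ordering it, because a one-decedent list has a predictable letter under alternation and section 6.2.1 has the same analysts record providers and track their status.
- **Section 6.3, odd lists:** give a rule carried across batches, for example the extra decedent alternating between letters within each stratum, with the first letter drawn at random.
- **Section 9.4.1:** add the strata actually used, and stratum-by-time terms, to equation [1]. The analysis then follows the randomisation and adjusts for chance imbalance in factors that predict change.

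The cost is protocol wording, slightly more allocation work and at most ten fixed-effect terms against about 384 decedents (six with four cells). No new data are needed. The gain in precision depends on how well the strata predict change, and may be small or zero.
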